#### 17.2.2 Analysis of Short Term HRQL Outcomes

We will use descriptive statistics (e.g., mean, standard deviation, median, ranges and interquartile ranges) to describe the overall FACT sum score and each domain score by treatment arm at each assessment period from baseline through the end of treatment. We will graph the data over the appropriate time frame similar to the analysis of the long term HRQL measures. This will inform us about the HRQL trajectories during treatment by treatment arm. If the data suggest it is reasonable we will calculate HRQL life years from areas under the curves and compare the treatment arms using ANCOVA or Wilcoxon test, as indicated by the data. We will examine missing data for systematic bias.

#### 17.2.3 Other Secondary Endpoints

Quantitative outcomes like number of retreatments and number of toxicities will be described by mean, standard deviations, median, minimum and maximum by treatment group and treatment group will be compared using a t-test. Categorical outcomes like any retreatment, any toxicity, radiologic response, pathologic response will be described by counts, percent and groups compared using the chi-square test. Overall survival, and 60 day post-transplant morbidity and mortality will be described by Kaplan-Meier estimates, and groups compared using the log-rank test and Cox model as for the primary outcome. Note, with 98 patients per arm, each arm will have 99% and 95% probabilities of observing at least one event of toxicity when the true probabilities per patient are 0.05 and 0.03. Further, when estimating proportion of patients to have a particular toxicity, the 95% confidence intervals will have precision of 10% or tighter, for each treatment group.

We will analyze secondary endpoints relating to time to event analogously to time to recurrence, and quantitative outcomes analogously to the analysis the HRQL endpoints.

### **Safety Measures**

Lab measures will be described and groups compared as described using t-tests or Wilcoxon tests as appropriate.

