## 7.0 Study Calendars

**Table 2: Study Calendar for SBRT (Arm A)**

Active Treatment-SBRT	Pre-Rx Eval  (screening)	SBRT fractions (5 in 2 week period) 	Last fraction of treatment (prior to discharge)	2 Week Follow up post treatment (+/- 3 days)
History and Physical Exam	X			X
Weight	X			X
CBC with differential	X 			X
AST, ALT, Alk Phos, Total Bilirubin, Albumin	X 			X
Na, BUN/Creatinine	X 			X
INR	X 			X

AFP (for HCC)	X 			
Toxicity Notation	X		X	X
Multiphasic MRI or CT of the abdomen within 4-6 weeks prior to enrollment	X			
Chest CT or Chest x-ray within 1 year prior to enrollment	X			
MELD-Na, ALBI, and CTP assessment	X 			X
HRQL 	X	X 	X	X
Randomization 	X			
Simulation	X			
Treatment: SBRT 		X (over a two week period)		

 Within 2 weeks prior to randomization unless otherwise specified

 If multiple lab results are available within the screening period, use the most recent results before randomization.

 If calculations are performed multiple times, use the most recent value before randomization

 HRQL questionnaire: FACT-Hep

 Randomization may occur after all screening procedures are complete and eligibility has been met. See section 3.0 for more details.

Initial treatment should be scheduled within 3 weeks of randomization.

See section 6.0 for details on HRQL administration timelines.

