**Table 4: Study Calendar for FOLLOW-UP (Both Arm A and Arm B)**

Follow-up After Initial Treatment Phase					
		3 months (+/- 4 weeks) post randomization	6 months (+/- 4 weeks) post Randomization	Q 3 months to 24 months post- randomization (+/- 4 weeks)	60 days post- transplantation (+/- 2 weeks)
History and Physical Exam		X	X	X	
Weight		X	X	X	
CBC with differential		X	X	X	
AST, ALT, Alk Phos, Bilirubin		X	X	X	
Na, BUN/Creatinine		X	X	X	
INR		X	X	X	
AFP (for HCC)		X	X	X	
Toxicity Notation		X	X	X	
Survival Status		X	X	X	X
MRI or CT of the abdomen  (mRECIST for HCC)		X	X	X	
Chest CT or X-ray 		X	X	X	
MELD-Na CP ALBI assessment		X	X	X	
Assessment of disease progression, recurrence and transplantation status		X	X	X	
HRQL 		X	X	X	
Mortality and Morbidity					X

 Scans will be obtained in accordance to liver transplantation protocols and timeframes and may not occur within the allotted time frame noted above. This will not be considered a protocol deviation as long as they are performed per United Network for Organ Sharing (UNOS) guidelines.

 HRQL questionnaire: FACT-Hep

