## 16.0 Sample Size

This study is sized for hypotheses testing of improved time to residual or recurrent disease within the previously treated lesion(s) due to SBRT versus TACE treatment arms in the overall population of patients who are eligible for liver transplant and are on the waiting list. It is believed that more than 50% of patients will receive a transplant within 2 years of listing, but that far fewer patients will receive

a transplant within 1 year of study begin. Therefore we base power calculations on one year follow up and a drop rate of 15%. Based on initial data, we estimate a median time to residual or recurrent disease of 134 days in the TACE group. Based upon these numbers and a hazard ratio of 0.6 for the SBRT relative to the TACE group, a two-sided test controlling the overall type 1 error to 5% requires a total of 161 events (i.e. residual/recurrent disease) and about 131 patients per treatment arm to achieve a power of 90%. To achieve a power of 80%, a total of 120 events and about 98 patients per treatment arm are required. These calculations are made accounting for follow-up on patients once every three months where the calculated HR of 0.6 for this discrete model corresponds roughly to a HR of 0.54 if recurrent disease could be measured on the continuous time scale (days).

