**Table 7 Sample Size Calculation**

HR	Median time  TACE (days)	Median Time  SBRT (days)	Power (%)	Nb of Events	Nb of patients per arm
0.6	134	223	90	161	131
0.6	134	223	80	120	98

 Median time is the median time to residual or recurrent disease.

Recruitment period of 365 days, duration of study of 2 years, yearly dropout rate of 15% (following exponential distribution), alpha=5%, two-sided test.

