## 17.0 Statistical Analysis

Baseline as well as post treatment measures will be summarized by descriptive statistics as appropriate such as mean, median, standard deviation, range and interquartile range. Comparison between treatment groups at baseline as well as changes from baseline will be made as appropriate using t-tests, Wilcoxon, chi-square and McNemar's tests as appropriate.

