### 17.2 Secondary Endpoints Analysis

#### 17.2.1 Analysis of Long term HRQL outcomes

The main HRQL outcome will be of the overall FACT sum score (FACT-G + FACT-Hep). The main analysis will be a random effects (repeated measures) analysis of the HRQL measures obtained using data taken at baseline, end of treatment, 2 weeks after treatment completion, and every 3 months thereafter (until 24 months). Depending on the amount of missing data at later time points, including for those patients who experience the primary outcome, are transplanted, or are loss to follow-up, the HRQL analysis may be truncated before 24 months (e.g., 12m months). For each patient the model will fit a random intercept and slope term. We will center time to the assessment time point nearest the center of

the time points of the data. Data will be inspected for linearity in time as well as constancy of variances. If the data show deviations from these linearity or constancy of variables we will attempt to remedy this through addition of nonlinearity terms or transformations.

The specific domains of HRQL that are impacted by the different treatments will be analyzed as secondary variables using the same analysis plan as the overall FACT score.

Additionally we will analyze both the primary (overall FACT score) and secondary (domain scores) long term HRQL measures in a descriptive manner both numerically (e.g. means, medians, standard deviations, ranges and interquartile ranges) comparing the groups, testing using analysis of covariance (ANCOVA accounting for baseline values) and graphically by plotting measures using jit plots, spaghetti plots (plots through time where individual patients data from multiple time points are connected with lines) and plots of the means or difference from baseline as estimated from the ANCOVA, or similar plots as suggested by the data. We will examine missing data for systematic bias.

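### Lab comparisons use t-tests or Wilcoxon, most naturally on change from baseline, with no baseline covariate; ANCOVA would be modestly more precise at no cost

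*Combined protocol and SAP*

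**What the plan says.** Lab measures have one sentence of their own, under Safety Measures in Section 17: "Lab measures will be described and groups compared as described using t-tests or Wilcoxon tests as appropriate". It names no lab, visit, scale or covariate, and it refers back to earlier text.

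Three other places bear on how it should be read:

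- Section 17.0, the general rule: "Comparison between treatment groups at baseline as well as changes from baseline will be made as appropriate using t-tests, Wilcoxon", among other tests.
- Section 17.2.3, last sentence, on secondary endpoints: "quantitative outcomes analogously to the analysis the HRQL endpoints".
- Section 17.2.1, on HRQL: a random-effects repeated-measures model and, in addition, "testing using analysis of covariance (ANCOVA accounting for baseline values").

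The data for adjustment will exist. Tables 2 and 3 schedule labs and MELD-Na, ALBI and CTP at screening in both arms, with a rule for choosing the baseline lab value: "If multiple lab results are available within the screening period, use the most recent results before randomization". Tables 2 and 3 repeat them two weeks after treatment. Table 4 repeats labs (including "AST, ALT, Alk Phos, Bilirubin") and the liver scores at 3 and 6 months and then every 3 months to month 24. Section 17 assigns no analysis to MELD-Na, CTP or ALBI.

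**The concern.** Neither a two-sample t-test nor a Wilcoxon test can take a baseline covariate. The plan accepts baseline adjustment for HRQL but does not carry it over to liver function, where a baseline value is equally available.

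Section 15.0 gives the trial a safety aim. Section 2.3 records MELD-Na, CTP and ALBI to help assess liver injury, Section 8.1 judges hepatic toxicity against each subject's own baseline, and Section 10.3 lists radiation-induced liver disease among possible long-term effects. A difference between arms in liver function is thus worth estimating as precisely as the data allow.

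Randomization is also stratified by CTP class (Section 3.0), and Appendix A builds CTP partly from bilirubin, albumin and INR. If a stratification factor predicts the outcome and is left out of the analysis, the standard error tends to be too large and the test conservative.

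At stake are some precision on supportive safety measures, and a choice of scale and test that the present wording leaves open.

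**Working it through.** **1. Which rule governs labs?**

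- Safety Measures names t-test or Wilcoxon and points back to something already described.
- Section 17.0 is the earlier text that pairs those two tests with between-arm comparison. It applies them to baseline values and to changes from baseline. For a post-treatment comparison, change is the natural reading.
- The sentence in Section 17.2.3 concerns secondary endpoints. Section B 2.0 lists toxicity among these, but not lab measures. The same section tests counts of retreatments and toxicities by t-test, so it does not clearly bring labs under the HRQL approach.

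The likely comparison is an unadjusted test of change scores. A test of raw follow-up values is possible but less likely.

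**2. The plan's own figures.** There is no power or precision figure for labs. The nearest is the toxicity statement in Section 17.2.3, with 98 per arm, and it reproduces:

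- 1 − 0.95^98 = 0.993 (stated 99%)
- 1 − 0.97^98 = 0.949 (stated 95%)
- 1.96 × √(0.25/98) = 0.099 (stated 10% or tighter)

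**3. Relative efficiency.** Assumptions, none given in the documents: equal SD σ at baseline and follow-up, correlation r between them, and complete data. The variance per patient entering the arm difference is:

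- raw follow-up value: σ²
- change from baseline: 2(1 − r)σ²
- ANCOVA: (1 − r²)σ²

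So ANCOVA relative to change is (1 − r²) / [2(1 − r)] = (1 + r)/2, and relative to raw values is 1 − r².

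| r (assumed) | ANCOVA / change | ANCOVA / raw | CI width, ANCOVA / change |
|---|---|---|---|
| 0.3 | 0.65 | 0.91 | 0.81 |
| 0.5 | 0.75 | 0.75 | 0.87 |
| 0.7 | 0.85 | 0.51 | 0.92 |
| 0.9 | 0.95 | 0.19 | 0.97 |

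In patients, the change-score test needs 2/(1 + r) times as many as ANCOVA: 1.33 at r = 0.5, 1.18 at 0.7 and 1.05 at 0.9. Equivalently, ANCOVA matches the precision of 98 per arm on change scores with 98 × 0.75 = 73.5, or 74, per arm at r = 0.5; 98 × 0.85 = 83.3, or 84, at 0.7; and 98 × 0.95 = 93.1, or 94, at 0.9.

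**4. Illustration in power.** The documents give no target lab difference. Take the standardized difference that gives 80% power on raw values at 98 per arm: (1.96 + 0.84) × √(2/98) = 0.40. Power for relative variance v is Φ(0.40/√(2v/98) − 1.96).

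| r | Raw | Change | ANCOVA |
|---|---|---|---|
| 0.5 | 80% | 80% | 90% |
| 0.7 | 80% | 95% | 97.5% |

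All of this concerns mean-based tests. The ratios are not the efficiency of ANCOVA against Wilcoxon, which the plan also allows.

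**The case against.** The strongest reply is that baseline is already used. A change score removes stable differences between patients, and Section 17.0 provides for change scores. This stands, and it limits the size of the point: for strongly correlated labs little is left to gain.

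A reader might instead infer that baseline is ignored and that raw follow-up values are compared, so that the test would need 1/(1 − r²) times the patients, or 1.33 to 1.96 times at r = 0.5 to 0.7. The documents do not support this as the main reading, because the Safety Measures sentence refers back and the matching earlier text concerns change.

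A second reply is that the last sentence of Section 17.2.3 may already put labs under the HRQL methods. It might, but labs are not a listed secondary endpoint and have their own heading and named tests. If that sentence is meant to govern, it conflicts with Safety Measures and the wording still needs repair.

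A third reply also stands: mean lab values are supportive and unpowered. The listed endpoint is toxicity, graded by CTCAE. Eligibility limits on bilirubin, INR and CTP score, together with stratification by CTP class, restrain the baseline spread and imbalance.

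**Conclusion.** The point holds as a modest efficiency gain. On the likely reading, ANCOVA variance is 75% to 85% of the change-score variance for an assumed correlation of 0.5 to 0.7, and 95% at 0.9. On the raw-value reading it is 75% to 51% for 0.5 to 0.7. The size rests on an assumed correlation, equal SDs and complete data. The power figures are illustrative, since subjects leave the study at local recurrence or transplant (Sections 5.6 and 12.2), and fewer than 98 per arm will contribute at later visits.

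Two stronger inferences should be avoided. First, a reader might conclude that chance baseline imbalance biases the planned tests. It does not: over the randomization both unadjusted comparisons are unbiased and valid, and chance imbalance is part of the variance already counted above. Second, a reader might conclude that MELD-Na and ALBI are to be compared without adjustment. The plan assigns them no test at all; the gap there is a missing analysis.

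**What to change.** Replace the Safety Measures sentence with a rule along these lines:

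- List the lab measures to be compared, and add MELD-Na and ALBI.
- Name the visits from Tables 2 to 4. For an on-treatment visit common to both arms, use two weeks after the last treatment, as Section 6.0 does for HRQL.
- Compare arms by ANCOVA at each visit, or by the HRQL repeated-measures model. Use the baseline value, CTP class and hepatitis C status as covariates. The HRQL model in Section 17.2.1 takes baseline as one of its repeated measurements; if it is adopted, enter baseline as a covariate and remove it from the outcomes.
- Analyze skewed labs on the log scale.
- State that this rule governs labs over the general text in Section 17.0 and the last sentence of Section 17.2.3.
- Keep the descriptive summaries.

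The cost is SAP wording, with no additional patients. One check is needed: Table 4 schedules ALBI, but its chemistry row does not list albumin, so confirm that albumin is recorded at those visits.

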### **Adverse events**

Adverse events will be described by body system and severity, on a per patient basis as well as a number per patient basis, and groups compared using chi-square and t-tests as appropriate.

## **18.0 Project Management, Data Management, and Site Monitoring**

Lahey Hospital & Medical Center (i.e., Sponsor) staff will accomplish all the tasks necessary for preparation and implementation of the project, including the drafting and refinement of the study protocol, development of the model consent document, assisting the PI in communications, developing project timelines, compiling required documents, preparing the detailed operations manual that outlines all the tasks required for study implementation at the sites, overseeing the distribution of documents, updating the protocol and operations manual as needed, updating regulatory files for the study overall, supervising the timely renewals of IRB approvals at the sites, and overseeing enrollment.

#### 18.1 Records to Be Kept

Each participating site will maintain appropriate medical and research records related to this trial in compliance with regulatory and institutional guidelines for the protection of subject confidentiality.

Source data are all information, original records of clinical findings, observations, or other activities in a clinical trial necessary for the reconstruction and evaluation of the trial. Examples of these original documents and data records include, but are not limited to hospital records, clinical and office records, laboratory notes, subjects' HRQL data, radiology records, and treatment related records.

#### 18.2 Role of Data Management

Lahey Hospital & Medical Center in conjunction with Quartesian will design and distribute source worksheets and the electronic data capturing system that will maintain all data collected as part of the protocol.

Data collection is the responsibility of the clinical trial staff at the site under the supervision of the site Principal Investigator. Collected study data must be promptly entered into the EDC system used by the Sponsor. Source worksheets should be used as the primary data collection instrument for the study, when possible. The investigator should ensure the accuracy, completeness, and timeliness of the data reported in the EDC and all other required reports. Data reported in the EDC, that are derived from source documents, should be consistent with the source documents and any discrepancies should be explained. Any missing data must also be explained. An audit trail will be maintained by the EDC system.

Sites are required to provide the Sponsor with de-identified source documents supporting the data entered into the EDC system within 1 week of each completed visit. Data must be shared via a Dropbox account approved by Lahey. If a site is unable to provide data via Dropbox, then an alternate method of data sharing maybe employed. Approved methods include mailing and faxing documents or through secure email.

All serious adverse events (SAE) (including death and hospitalization), premature withdrawal, and emergency treatment disclosures must be reported to the project program manager and [name] at the Lahey Hospital & Medical Center within one working day of site becoming aware of the event. Sites will notify [name] and the project program manager by emailing [[contact]](mailto:[contact]). Please include Site Name, Patient study ID, SAE event term, grade and pertinent de-identified source documents. Applicable SAE forms should be completed in the electronic data capture system (EDC) within one week of their occurrence and updated as new information becomes available.

A data monitoring committee comprised of [name] along with two Co-Investigators from Lahey Hospital will review all Adverse Events on a quarterly basis. All Serious Adverse Events will be reviewed as they occur in real time.

### **18.3 Data Verification & Quality Assurance**

The site monitoring, regulatory review, adverse event reporting and quality assurance issues will be overseen by Lahey Hospital & Medical Center. Each site will permit authorized representatives of the sponsor and regulatory agencies to examine (and when required by applicable law, to copy) clinical records for the purposes of quality assurance reviews, audits and evaluation of the study safety and progress. The Coordinating Center at Lahey will review and track Adverse Events, Serious Adverse Events, and Unanticipated Problems.

Centralized remote monitoring will be carried out by Coordinating Center at Lahey Hospital & Medical Center. Monitoring will occur through periodic review of submitted source data and data in the EDC system. A sample of enrolled patients may be randomly selected for a focused comprehensive audit of all data. Depending on enrollment progress, the goal will be to audit a 10% sample of enrolled patients from each site involved. The audit will be performed by comparing data submitted through the EDC against source documentation submitted by the site. If a greater than 10% error rate is discovered, an additional 10% sample will be selected to audit. Additional auditing may be initiated per the Sponsor's discretion.

## **19.0 Human Subjects**

### **19.1 Institutional Review Board (IRB) Review and Informed Consent**

Informed consent must be obtained prior to performing any study specific procedures. The consent form will describe the purpose of the study, the procedures to be followed, and the risks and benefits of participation. A copy of the consent form will be given to the subject or legal guardian, and this fact will be documented in the subject's record.

This protocol and corresponding informed consent document and any subsequent modifications will be reviewed and approved by the IRB responsible for oversight of the study. A signed consent form will be obtained from each subject prior to any study intervention. For subjects who cannot consent for themselves, a legal guardian, or person with power of attorney, must sign the consent form in accordance with institutional policies and state laws; additionally, the subject's assent must also be obtained if he or she is able to understand the nature, significance, and risks associated with the study.

### **19.2 Subject Confidentiality**

All laboratory specimens, source documents case report forms, and other records that leave the site will be identified only by the SID to maintain subject confidentiality. All computer entry and networking programs will be done using SIDs only. Identifiable clinical information will not be released without written permission of the subject, except as necessary for monitoring by the study monitor, IRB, the sponsor, or the sponsor's designee.

### **19.3 Study Modification/Discontinuation**

The study may be modified or discontinued at any time by the sponsor or IRB as part of their duties to ensure that research subjects are protected.

